##### 4.3 Exclusion criteria

A potential subject who meets any of the following criteria will be excluded from participation in this study:

1. Any concurrent illness, disability or clinically significant abnormality that may, as judged by the investigator, affect the interpretation of clinical efficacy or safety data or prevent the subject from safely completing the assessments required by the protocol.
2. Non-diabetic renal disease e.g. known polycystic kidney disease.
3. Use of LMW heparin and/or immunosuppressive drugs.
4. Significant food allergies for galactose, nuts, soy, tomato, corn, grape, melon and artichoke, which would make the subject unable to consume the food provided.
5. Signs of active infection or autoimmune disease, requiring systemic treatment.
6. A psychiatric, addictive or any disorder that compromises ability to give truly informed consent for participation in this study.

7. Malignancy (including lymphoproliferative disease) within the past 2-5 years (except for squamous or basal cell carcinoma of the skin that has been treated with no evidence of recurrence).
8. Use of any other investigational drug.
9. Patient has enrolled another clinical trial within last 4 weeks.

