Marine organism-derived fucosylated and sulfated polysaccharides that mimic glycosaminoglycans may have beneficial effects in diabetic patients by stabilizing the imbalanced glycocalyx. Fucoidan, extracted from brown seaweed, is one of those sulfated polysaccharides and is the main component of the food supplement Endocalyx™. Administration of the supplement in a mouse model of aging revealed beneficial vascular effects by reducing mesenteric macrophage accumulation and increasing capillary density. Moreover, daily administration of Endocalyx™ in healthy volunteers improved the quality of the endothelial glycocalyx, measured with SDF-imaging, compared to no treatment (unpublished data, [name]).

Simultaneously, the Longo group showed that a monthly cyclic 5-day periodic fasting mimicking diet (FMD) was able to rejuvenate the immune system, decrease tissue inflammation and extend life- and health span. In experimental studies, a fasting mimicking diet improved insulin sensitivity and reduced circulating inflammatory cytokines, which are involved in sustained activation of endothelial cells [37, 38]. Furthermore, two clinical trials revealed long lasting beneficial effects after 3 monthly FMD cycles on metabolic parameters (fasting glucose, systolic blood pressure and blood IGF-1 levels) and systemic inflammation in subjects with a high cardiovascular risk at baseline [38, 39].

This fasting mimicking diet may lead to beneficial effects in the diabetic kidney by several mechanisms. First, amelioration of glucose levels will decrease the amount of glycated serum proteins, which are one of the most potent inducers of heparanase. In addition, fasting induces upregulation of intra-glomerular autophagy [40]. Autophagy is a highly regulated lysosomal protein degradation pathway that removes protein aggregates and damaged or excess organelles to maintain intracellular homeostasis and cell integrity. Impairment in autophagy is thought to be involved in the pathophysiology of diabetic nephropathy and contributes to endothelial dysfunction [41-43]. Hyperglycaemia upregulates autophagy in several renal cell types such as mesangial cells, endothelial cells, and podocytes. However,

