#### 6.5.2 Food supplement

##### Composition of one Endocalyx capsule

Ingredient	Amount (mg/capsule)
Fucoidan (85%)	106.25 mg
Oxxyne OMD-MVHS Blend SOD (Superoxide dismutase, catalase and polyphenols)	120.00 mg
Glucosamine Sulfate	375.00 mg
Hyaluronic Acid 1800-3000 kDa	17.50 mg
Microcrystalline Cellulose	130.00 mg
Silicon Dioxide	2.00 mg
Total mg per capsule	750.75 mg

Fucoidan is a fucosylated and sulfated polysaccharide extracted from the brown algae species *Laminaria japonica* that mimics heparan sulfate, the main glycosaminoglycan of the endothelial glycocalyx.

Hyaluronan or hyaluronic acid is also a glycosaminoglycan that is incorporated in the endothelial glycocalyx.

Oxynea OMD-MVHS Blend SOD contains superoxide dismutase (SOD) and polyphenolic enzymes extracted from olive, grape and artichoke. These enzymes act as antioxidants, capable of helping to prevent cellular and molecular damage caused by free radicals, such as reactive oxygen species, through scavenging the oxidants and inhibiting further activity.

Glucosamine sulfate is extracted from corn, and is an amino sugar and precursor in the biochemical synthesis of glycosylated proteins and lipids. It can increase synthesis of two main constituents of the endothelial glycocalyx, namely heparan sulfate and hyaluronan.

Silicon dioxide and microcrystalline cellulose are natural anti-caking agents used to prevent the components from sticking together.

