### 10.3 Benefits and risks assessment, group relatedness

The prevalence of type 2 diabetes is high in South Asian patients [22]. These patients have a 40 times higher risk of developing ESRD and a faster progression to renal failure compared to West European patients [54]. This is may be linked to increased systemic and glomerular inflammation in these patients [24, 55, 56]. Consequently, these patients will probably have an impaired endothelial glycocalyx with high heparanase activity and would benefit the most from treatments that support the glycocalyx homeostasis and reduce inflammation burden. To date, treatments for diabetic nephropathy are insufficient in preventing the development of ESRD. The interventions in this study can be used as add-on dietary interventions to reduce residual albuminuria and progression of renal disease.

The intervention burden in the FMD arm is for 5 days a month and in the other arms by taking daily capsules. Blood and urine sampling and non-invasive SDF imaging will be done at 3 time points in all intervention groups. In addition, patients are frequently monitored due to the possible effects of the interventions on glucose levels and insulin sensitivity. For the FMD group this means frequently measuring glucose values trough a finger prick.

Patients in the diet group have a risk of the occurrence of hypoglycemia during the study. In the days of the diet, this risk is reduced by stopping the hypoglycemic drugs that can cause hypoglycemia. After the diet, patients are asked to measure their glucose levels regularly.

The dosages of the hypoglycemic drugs can be altered if needed.

Other risks of the interventions may be an allergic reaction to one of the components of the diet or the food supplement. However, if eligible patients already are known with specific food allergies, they are excluded from the study. Effects on kidney function and liver function will be monitored during the study, but are not expected as a result of the interventions. In our opinion, the risk of the interventions is reduced within our study design and therefore the limited side effects and possible beneficial effects of the interventions on metabolic parameters, microvascular health and albuminuria justify participation in this study.

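### The closed food-allergy list in exclusion 4 omits brown algae and olive, two of the five plant or algal capsule sources named in Section 6.5.2, although Section 10.3 relies on known food allergies being excluded

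*Combined protocol and SAP*

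**What the plan says.** Section 4.3, exclusion 4, rules out patients with "Significant food allergies for galactose, nuts, soy, tomato, corn, grape, melon and artichoke, which would make the subject unable to consume the food provided". Nothing in it marks the list as examples, whereas exclusion 2 in the same section introduces its example with e.g.

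Section 6.5.1 names nuts, soy and tomato as ingredients of the diet.

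Section 6.5.2 gives the natural sources of the capsule's active ingredients:

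- On fucoidan: "Fucoidan is a fucosylated and sulfated polysaccharide extracted from the brown algae species" *Laminaria japonica*.
- On the antioxidant blend, superoxide dismutase together with "polyphenolic enzymes extracted from olive, grape and artichoke".
- On the amino sugar: "Glucosamine sulfate is extracted from corn".

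Section 1 describes fucoidan in these words: "extracted from brown seaweed, is one of those sulfated polysaccharides and is the main component of the food supplement Endocalyx™".

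Section 10.3 lists an allergic reaction to a component of either product among the risks. It answers that risk by stating that "if eligible patients already are known with specific food allergies, they are excluded from the study".

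**The concern.** Exclusion 4 is the only criterion that mentions allergy, and it overlaps heavily with the ingredient descriptions in Section 6.5. Against those descriptions it is incomplete. Olive shares a phrase with grape and artichoke in Section 6.5.2, yet only the latter two reach the list. Brown algae is also missing.

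What is at stake is the consistency of the safety argument. Sections 6.4.1 and 6.4.2 describe the remaining allergy risk as a reaction that was not previously known. That description fits only if known allergies to the ingredients have been screened out. For brown algae and olive the written criterion does not do so.

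The protocol treats an allergic reaction as a reason for withdrawal (Sections 7.4 and 12.1j) and plans for severe cases (Section 5.4). Under Section 7.6 a withdrawn patient has no further study follow-up beyond usual general practitioner care and follow-up of the adverse event. An avoidable reaction before month 3 would therefore also cost a primary-endpoint value in an arm of 30.

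**Working it through.** **Capsule composition (table in Section 6.5.2).** The plan's total reproduces:

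106.25 + 120.00 + 375.00 + 17.50 + 130.00 + 2.00 = 750.75 mg.

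Four capsules a day give 4 × 750.75 = 3003 mg, which agrees with the 3 grams in Section 6.6.2.

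**Sources set against exclusion 4.** The text of Section 6.5.2 names five plant or algal sources. Share of mass is the ingredient's mg divided by 750.75.

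| Capsule ingredient | Named source | mg per capsule | Share of mass | In exclusion 4? |
|---|---|---|---|---|
| Glucosamine sulfate | corn | 375.00 | about 50% | yes |
| Antioxidant blend | grape | 120.00 (whole blend) | about 16% (whole blend) | yes |
| Antioxidant blend | artichoke | within the same 120.00 | – | yes |
| Antioxidant blend | olive | within the same 120.00 | – | **no** |
| Fucoidan | brown algae | 106.25 | about 14% | **no** |

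Three of five are listed and two are not. Fucoidan intake is 4 × 106.25 = 425 mg per day, in line with the roughly 400 mg given in Section 12.1e.

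**Diet.** Nuts, soy and tomato (Section 6.5.1) are all in exclusion 4: three of three.

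**Remaining entries.** Galactose and melon are in exclusion 4 but are not named in Section 6.5.1 or 6.5.2. The list is therefore not a plain copy of those sections, and the protocol does not say how it was compiled.

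**Section 10.3 against exclusion 4.** The reference there to specific food allergies can be read in two ways:

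1. It means the allergies listed in exclusion 4. The statement is then true, but it covers less than the risk it is meant to answer, which is a reaction to any component of the diet or supplement.
2. It means any known allergy to a product component. Exclusion 4 then does not carry out what Section 10.3 states.

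On either reading, brown algae and olive are left uncovered.

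**Size.** No document gives the prevalence of seaweed or olive allergy in this population, so the expected number of patients cannot be calculated. One affected patient in the supplement arm is 1/30 = 3.3% of that arm.

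**The case against.** The strongest reply is that other provisions could keep such a patient out:

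- Exclusion 1 lets the investigator exclude any abnormality that may affect the interpretation of safety data or prevent safe completion of the assessments.
- Inclusion 9 requires the ability to meet the protocol's requirements, which include four capsules a day.
- Relevant medical history is taken under the baseline characteristics in Section 7.3.
- Section 10.3 itself shows an intention to exclude patients with known allergies.

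This stands in part. A reader might infer from the gap that a patient with a known seaweed or olive allergy would simply be randomised. The documents do not support that, because an attentive investigator has grounds to refuse. But these provisions are general and none names allergy. The documents also show no screening question about seaweed or olive. They make an error less likely without completing the list.

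A second tempting reading is that the list picks up trivial ingredients and misses the principal one. That is not supported either. Corn, which is listed, is the source of about half the capsule mass. Calling fucoidan the main component is Section 1's description; by mass it ranks below both glucosamine sulfate and the antioxidant blend. Brown algae and olive are named as sources in the text of Section 6.5.2, not as rows of the composition table.

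Third, the documents do not say whether someone allergic to seaweed or olive would react to the extracts in the capsule. Section 12.1e summarises human fucoidan studies without reporting allergic reactions, but it does not say whether people with a known seaweed allergy took part. The wording at the end of exclusion 4, about being unable to eat what is provided, also suits the diet better than capsules. That is a further reason to revisit the criterion.

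**Conclusion.** The point holds as an inconsistency between an eligibility criterion and the risk section. Exclusion 4, read literally, covers three of the five capsule sources named in Section 6.5.2 and all three named diet allergens, and it leaves out brown algae and olive. Section 10.3 treats known food allergy as dealt with, and for these two sources only general clauses stand behind that statement.

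The conclusion rests on reading exclusion 4 as a closed list, which its wording supports. It makes no claim about how often such allergies occur, how likely a reaction to the extracts is, or whether an affected patient would in practice be enrolled.

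The weight is low. The number of patients is not given and is probably very small, and nothing in the sample size, significance level or analysis depends on it. It is worth correcting because it concerns patient safety and costs almost nothing.

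**What to change.** Reconcile Sections 4.3, 6.5.2 and 10.3. The allergy criterion, and a matching question at screening, should cover every source that the protocol names for the capsule and the diet, including brown algae (seaweed) and olive. The closing words of exclusion 4 should apply to the capsules as well as the food. Section 10.3 should then refer to exclusion 4 directly. If the sponsor left either source out deliberately, Section 10.3 should give the reason and should no longer imply that known allergies to all components are excluded.

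The cost is one line in the criteria, one line on the screening form and possibly a very small number of extra exclusions. The sample size and the analysis do not change.

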#### **4.4 Sample size calculation**

The primary outcome will be improvement of the Microvascular Health Index after 3 months. The sample size is chosen according to a pilot study with 13 healthy volunteers receiving the food supplement Endocalyx™ for 3 consecutive months. After 3 months, a 31% improvement in Microvascular Health Index was demonstrated, expressed in a significant increase of the MHI from 1.05 at baseline, to 1.38 at 3 months (improvement of 0.33).

Group sample sizes of 23 per group achieve 80% power to detect a difference of 0.35 between the null hypothesis that group improvement means are 0.0 and the alternative hypothesis that the improvement mean of group 2 or 3 is 0.35 with estimated group standard deviations of 0.41 with a significance level (alpha) of 0.05000 using a two-sided two-sample t-test. If we anticipate a 25% drop out rate per group, we will need 30 patients per group.

Therefore, we decided to enrol a total number of 90 patients in this study.

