## 6.3 Summary of findings from clinical studies

### 6.3.1 Fasting mimicking diet

The Longo group developed Prolon, a plant based low-protein low-caloric 5-day fasting mimicking diet for humans. This intermitting short period of fasting obtains the beneficial effects on IGF-1, inflammation, glucose and insulin levels similar of water fasting, while providing micronutrients to minimize the burden of fasting.

In a pilot study, 19 healthy volunteers followed this diet for 5 days per month for 3 consecutive months. At the end of the first 5-day cycle, fasting glucose, IGF-1 levels and body weight were significantly reduced and these effects remained after resuming a normal diet, one week after finishing the third cycle. As a marker for systemic inflammation and risk factor for cardiovascular disease, C-reactive protein levels were measured. For subjects with CRP levels in the moderate to high risk range at baseline, levels returned within the normal range after 3 FMD cycles [38].

After that, a larger randomized cross over trial with the Prolon diet was conducted with 71

healthy individuals that completed 3 cycles of the diet in 3 months. A significant reduction in BMI, total body fat, systolic blood pressure, and serum IGF-1, total cholesterol, HDL and LDL levels was seen one week after finishing the third FMD cycle. A post hoc analysis that stratified the effects of the diet by risk factor showed that only for subjects with prediabetic fasting glucose levels ( $>99$  mg/dL) and for subjects with high CRP levels ( $>1.0$  mg/L) at baseline, levels returned to normal ranges 5 days after finishing the third FMD cycle. Moreover, a voluntary follow-up 3 months after finishing the third FMD cycle showed that the significant beneficial effects on body weight and inflammation remained in all follow-up subjects. For subjects with at-risk levels at baseline, fasting glucose, IGF-1 levels and the systolic blood pressure were still significantly reduced 3 months after finishing the last FMD cycle, indicating that the beneficial effects of the diet may last for several months [39]. In conclusion, the fasting mimicking diet has a long lasting positive effect on metabolic factors but also obtains anti-inflammatory effects in subjects with a high cardiovascular risk profile.

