### 6.3.2 Food supplement

A pilot study was conducted among 13 healthy volunteers receiving the Endocalyx food supplement. After 3 months, the Microvascular Health Index measured by SDF imaging improved by 31%. After 4 months, the Microvascular Health Index in the volunteers improved by 50%. This showed the beneficial effects of the food supplement on the microvasculature as it significantly increased capillary density and red blood cell filling percentage, and reduced the perfused boundary region (unpublished data, [name]).

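### Section 4.4 rests the sample size on a pilot improvement of 0.33 but computes with an unexplained 0.35; at 0.33, 23 completers per arm give about 76% power

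*Combined protocol and SAP*

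**What the plan says.** Section 4.4 names its basis: "The sample size is chosen according to a pilot study with 13 healthy volunteers receiving the food supplement". It reports the pilot result as a 31% improvement, "expressed in a significant increase of the MHI from 1.05 at baseline, to 1.38 at 3 months (improvement of 0.33"). Section 6.3.2 gives the same three-month result: "After 3 months, the Microvascular Health Index measured by SDF imaging improved by 31" percent.

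The next paragraph of 4.4 states the calculation: "Group sample sizes of 23 per group achieve 80% power to detect a difference of 0.35". The null hypothesis is that "group improvement means are 0.0 and the alternative hypothesis that the improvement mean of group 2 or 3 is 0.35". The other inputs are a standard deviation of 0.41 in each group and a two-sided two-sample t-test at alpha 0.05. The number to enrol follows: "If we anticipate a 25% drop out rate per group, we will need 30 patients per group", which makes 90 in total.

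Section 7.5 confirms the aim of 23 completers per group. It counts protocol violators together with drop-outs in the 25%, and it allows some drop-outs in the first two and a half months to be replaced. Section 9.1 plans an independent t-test of the change in MHI for each active arm against placebo, by intention to treat, so the planned test matches the one in 4.4.

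**The concern.** Two consecutive paragraphs of 4.4 give two effect sizes. The first offers 0.33 as the basis for the sample size. The second powers the trial for 0.35 without saying why. Rounding does not explain it: 0.33 is already given to two decimals, and 31% of 1.05 is 0.33, whereas 0.35 is 33% of 1.05. The only other pilot figure, a 50% improvement at four months in 6.3.2, does not lead to 0.35 either.

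The change goes in the favourable direction, because a larger assumed effect needs fewer patients. Someone who reads 4.4 and later sees a null result will take it that each comparison had 80% power at the effect seen in the pilot. With 23 analysed per arm it would have had about 76%, so a true difference of that size would be missed about 24% of the time rather than 20%.

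**Working it through.** **Inputs, all from section 4.4:** SD of the change 0.41 in each group; two-sided alpha 0.05; two-sample t-test; placebo change 0.0; difference either 0.35 (used in the calculation) or 0.33 (the pilot result); 23 per group after drop-out; 30 enrolled per group.

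**Effect sizes as percentages of the pilot baseline.** 1.38 − 1.05 = 0.33. 0.33 / 1.05 = 31.4%, which agrees with the stated 31%. 0.35 / 1.05 = 33.3%, which does not.

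**Formula.** With n analysed per arm, the standard error of the difference is SE = 0.41 × √(2/n), the noncentrality is the difference divided by SE, and df = 2n − 2. Power is the probability that a noncentral t variable with that df and noncentrality falls beyond the two-sided 5% critical value.

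**Step 1, the plan's own figure.** For n = 23, SE = 0.41 × √(2/23) = 0.1209, df = 44 and the critical value is 2.015. Noncentrality = 0.35 / 0.1209 = 2.895. Power = 80.8%. With 22 per arm it is 79.0%, so 23 is the smallest whole number that reaches 80%. The plan's figure reproduces.

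**Step 2, the pilot value.** With the same SE, noncentrality = 0.33 / 0.1209 = 2.729. Power = 76.1%, and the miss rate is 100 − 76.1 = 23.9%.

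**Step 3, power by number analysed per arm:**

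| Analysed per arm | Power at 0.35 | Power at 0.33 |
|---|---|---|
| 22 | 79.0% | 74.2% |
| 23 | 80.8% | 76.1% |
| 25 | 84.1% | 79.6% |
| 26 | 85.5% | 81.2% |
| 30 | 90.2% | 86.5% |

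The smallest number giving 80% at 0.33 is 26. The smallest difference with 80% power is 0.346 with 23 per arm and 0.355 with 22. Both are above 0.33.

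**Step 4, drop-out.** 30 × 0.75 = 22.5, and 23 / 0.75 = 30.67, which rounds up to 31. So 30 per arm with exactly 25% loss leaves 22 or 23. The difference between those is 80.8 − 79.0 = 1.8 points at 0.35 and 76.1 − 74.2 = 1.9 points at 0.33.

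**Step 5, loss at which the gap closes.** 26 of 30 analysed means 4 lost, and 4 / 30 = 13.3%.

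**Step 6, dependence on the SD.** With 23 per arm and a difference of 0.33, power reaches 80% if the SD is 0.39 rather than 0.41.

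**The case against.** The strongest reply is that the stated calculation contains no error. The plan claims 80% power only at 0.35, and that claim is correct. A reader might infer from the 76% figure that the sample size was miscalculated or that the trial is materially underpowered. The documents support neither reading. Choosing the size with a pilot in mind does not oblige the planners to use its point estimate, and one common detectable difference for two active arms is a usual choice. This part of the reply stands. What remains is that 4.4 cites 0.33 as its basis, departs from it and does not say so.

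Second, a gap of 0.02 is small on an index that runs from 0 to 10, when the estimate comes from 13 people. That is true, and the size of the SD matters as much (Step 6). It bears on how serious the point is, not on whether the two figures agree.

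Third, the figures for 22 completers are the low end. Section 7.5 allows some replacement in order to reach 23, although this is discretionary and limited by reason and timing. The 25% also includes protocol violators, and those with a month-3 MHI can stay in the intention-to-treat analysis. This stands too. The main figure is therefore the one at 23, and more may be analysed.

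A reader might also infer that the plan hides an assumption of no placebo response, because the pilot figure is a change from baseline in volunteers on the supplement. It does not: 4.4 writes the null improvement as 0.0 and gives the alternative to the active groups only. Section 1 also reports that the supplement "in healthy volunteers improved the quality of the endothelial glycocalyx, measured with SDF-imaging, compared to no treatment", though without an MHI difference and without saying whether this is the same pilot. Nor is it an internal contradiction that the diet studies in 6.3.1 report metabolic and inflammatory results, such as "A significant reduction in BMI, total body fat, systolic blood pressure, and serum IGF-1, total cholesterol, HDL and LDL levels was seen", and no MHI. That gap, like the unstated source of the SD, is missing detail and not a wrong figure.

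**Conclusion.** The point holds in a limited form. Section 4.4 attributes its sample size to a pilot improvement of 0.33, computes with 0.35 and gives no reason. Its 80% is right for 0.35. At the pilot value, power per comparison is about 76% with 23 completers per arm, a gap of 80.8 − 76.1 = 4.7 points, and 80% would need three more completers per arm. The gap disappears if at least 26 of 30 per arm are analysed, that is, if loss is about 13% or less against the planned 25%. The drop-out rounding adds under 2 points of uncertainty.

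These figures rest on the plan's own assumptions: SD 0.41 in each arm, no MHI change on placebo, and a two-sided 5% test for each comparison. They do not show that the trial is too small or its analysis unsound. They show that the stated power does not apply to the effect cited as its basis.

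**What to change.** Keep 30 patients per arm and leave the analysis unchanged. In section 4.4:

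- State power per comparison with 23 completers as about 80% at 0.35 and about 76% at the pilot's 0.33, and with 22 completers as about 79% and 74%.
- Present 0.35 as an assumed detectable difference for both interventions, and not as the pilot estimate. The pilot can stay as background.
- Say that 30 less 25% leaves 22 or 23 per arm.

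The change is a few sentences, with no extra patients. Its cost is a slightly less favourable stated power at the pilot value. The restated figures may prove cautious if fewer than 25% are lost.
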